7.4 Study Design

7.4.1 Selection and randomization of volunteers

Medical personnel at the outpatient clinic of Saratov Institute of Cardiology will be informed about implementing the study, its major goal and selection criteria for volunteers. Suitable individuals will be invited for preliminary check-up (physical and laboratory investigation) during the initial phase of enrolment. All suitable individuals will be re-screened after the wash-out period of the study before the final decision on study enrolment is made.

Randomization of volunteers in the study will be performed using widely accepted methods such as simple randomization and stratified randomization. Briefly, the

software containing a random number generator will be applied to the database of volunteers. The assigned group will be considered as final. The groups will be balanced according to numerical age and gender with special software. Stratified randomization will be used to enhance statistical strength of the final results and will ensure equality of groups for secondary selection criteria.

7.4.2 Schedule of Procedures/Evaluations

All medical evaluations will be performed in a window of time from 0-15 days of study initiation. This includes anamnestic evaluation with preliminary physical and laboratory investigation. All volunteers will be re-screened at the "0" time point of the study.

7.4.3 Study Duration

Interventional period is designed to last for 1 month. It will be preceded by the enrolment period.

Inclusion Criteria

Major inclusion criteria are as follows: Caucasian male or female subjects 50-70 years old, overweight with BMI more than 30 and less than 35 kg/m², absence of concomitant intake of anti-hypertensive, lipid-lowering or

any other cardio-vascular drugs, vitamin supplements and any specific dietary interventions.

7.4.4 Exclusion Criteria

Among exclusion criteria are: inability to comply with the study protocol, severe medical conditions (hepatitis, pancreatitis, uncontrolled diabetes, cancer, recent cardiovascular events, tuberculosis etc.), history of alcohol abuse or alcoholism, participation in other clinical trials and intolerance of cocoa-based or lycopene-containing products.

7.4.5 Wash-out period

The volunteers will be asked to refrain from consumption of cocoa and tomato based products for 14 days before beginning the study.

7.4.6 Mode of intake

The volunteers will be asked to take the study products, one 10 gram bar of lycosome formulated DC, 1st arm, or one 10 gram bar of regular DC, containing no lycopene, 5th arm, once a day in the evening with the main meal for 1 month.

Volunteers from the 2nd arm of the study will be requested to take a capsule containing 7 mg of lycopene, an amount equal to the quantity of lycopene in the 10 g bar of lycosome formulated DC.

Volunteers in the 3rd arm will be asked to take capsules with 30 mg lycopene in cocoa butter, and in the 4th arm 30 mg of lycopene in sunflower oil.

All interventional products are to be ingested once a day in the evening with the main meal for 1 month.

8. STUDY DRUG STORAGE AND ACCOUNTABILITY

The Principal Investigator and Medical Officer of the study are responsible for ordering, receiving, and tracking inventory; storing,

dispensing, and returning study products properly; and, where necessary, labeling of study products prior to dispensing according to protocol guidelines and good manufacturing practices (GMPs). All study products supplied for the protocol will be accounted for and tracked in a manual or electronic accountability log for the study. Accountability for the study products will be documented from the time of initial receipt through dispensation and final disposal of leftover study products. The accountability log will indicate the date, amounts, batch numbers, and condition upon receipt of all materials received. Upon study completion, remaining study products will be returned or destroyed as defined by specific Principal Investigator instructions, or other documented instructions. The balance returned or sent for destruction will be recorded in the study accountability log. Quality assurance reviews and inspection of study products and accountability documentation will be performed at intervals during the study by a Clinical Monitor. Study products will be stored at the clinical site facility in a locked cabinet.

9. STUDY PRODUCT COMPLIANCE AND ADHERANCE

Compliance of volunteers to the protocol and adherence to the wash-out period will be determined by questioning the volunteers during the intermediate and final visits to the clinical site and by random private phone calls. Volunteers with poor adherence to the study protocol will be withdrawn from the study by the Medical Officer.

10. Concomitant Medications

Patients with concomitant intake of anti-hypertensive, lipid-lowering or any other cardiovascular drugs are not eligible for the study.

11. Safety and Effectiveness Assessments:

Safety assessment procedures are barely applicable since widely consumed food products will be used for the study. Volunteers with DC and tomato product intolerance will not be enrolled for the study.

Effectiveness assessment will be by biochemical and bacteriological analysis following ingestion of study products.

11.1 Safety assessments

The volunteers will be instructed to look out for the appearance of skin rash, nausea or dyspepsia and to report any of these to the Medical Officer should they occur.

11.2 Effectiveness assessments

Measurements of gut microbiota spectrum and markers of oxidation in blood will be used for effectiveness assessment.

12. Adverse Event Reporting:

Occurrence of adverse events in volunteers consuming lycopene or DC is very unlikely. Should any occur it is the responsibility of the Medical Officer and the Principal Investigator to determine and analyze adverse reaction cause.

Adverse reactions following lycopene formulated DC product intake can include skin rashes, dyspepsia, transient increase of blood pressure, abnormalities in sleep.

Occurrence of any of these events will be considered as a reason for volunteer withdrawal from trial participation.

12.1 Recording/Reporting requirements

Each of the volunteers will be required to report any possible adverse effect to the Medical Officer assigned to the study, whose responsibility is to immediately inform the Principal Investigator about any possible adverse reaction. Moreover, appropriate information will be immediately passed on to the Local Ethical Committee. All observed or volunteered adverse events

(serious or non-serious) and abnormal test findings, regardless of study group or suspected causal relationship to the study will be recorded in the subject case histories. Adverse events or abnormal test findings felt to be associated with the study will be followed up until the event (or its sequelae) or the abnormal test finding resolves or stabilizes.

For all adverse events, sufficient information will be pursued and/or obtained so as to permit 1) an adequate determination of the outcome of the event (i.e., whether the event should be classified as a *serious adverse event*) and; 2) an assessment of the casual relationship between the adverse event and the study products.

An abnormal test finding will be classified as an *adverse event* if one or more of the following criteria are met:

- The test finding is accompanied by clinical symptoms
- The test finding necessitates additional diagnostic evaluation(s) or medical/surgical intervention; including significant additional concomitant drug treatment or other therapy

Lycotec Ltd and the Saratov Institute of Cardiology will promptly review documented adverse events and abnormal test findings to determine 1) if the abnormal test finding should be classified as an adverse event; 2) if there is a reasonable possibility that the adverse event was caused by the study products; and 3) if the adverse event meets the criteria for a *serious adverse event*.

If the final determination of causality is “unknown and of questionable relationship to the study product”, the adverse event will be classified as *associated with the use of the study product* for reporting purposes. If the Sponsor-Investigator’s final determination of causality is “unknown but not related to the study product”, this determination and the rationale for the determination will be documented in the respective subject’s case history.

12.2 Withdrawal of subjects due to adverse events

Any subject with adverse reaction and/or abnormal laboratory test findings will be withdrawn from the study by the Medical Officer and replaced with an eligible volunteer from the pre-screened pool of volunteers. An appropriate report to the Local Ethical Committee will be filed.

13. Statistical Methods/Data Analysis: 9.1

Study endpoint

For assessment of normally distributed parameters the Shapiro-Wilk method will be used. Student's t-test will be applied both for paired and unpaired samples. Between-group differences at one time point will be evaluated by Wilcoxon-Mann-Whitney test (continuous variables) and Fisher's Exact test (categorical variables). Data analysis will be performed using Stata SE, version 12.1. All statistical tests are two-sided and statistical significance level alpha will be set at 0.05 for the analysis.

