The interventional procedure will be conducted stringently according to the conditions described in the protocol approved by the Institutional Review Board. In particular, volunteers will be given the study products over two separate visits for a total of one month's supply. To assess effect of lycosome-formulated DC volunteers from the first arm will be given lycosome-formulated DC containing 7mg lycopene while volunteers from the fifth arm will be given the regular formulation of DC without lycopene. Volunteers from the second arm of the study will be given capsules containing 7 mg of lycopene, this amount is equal to the amount of lycopene ingested daily with lycosome-formulated DC. Investigational products will be given to volunteers twice – at the "0" time point of the study and at the intermediate time point (two weeks after study initiation). To assess dose-dependency and effect of fat matrix volunteers from the third and fourth arms will be given 30 mg of lycopene in either cocoa butter or sunflower oil.

Upon arrival at the study site all volunteers will be asked about current health status and will undergo scrupulous anamnestic, physical and laboratory investigations. Each of these procedures will be conducted by

highly trained medical professionals including nurses and practicing physicians.

Study products will be given immediately after all evaluations are complete.

Lycosome formulation of DC is a proprietary formulation of DC (Lycotec Ltd, Cambridge, UK) with enhanced bioavailability of lycopene and cocoa flavanols in which the flavanols are protected from oxidation by a lycopene coat and embedded into cocoa butter micelles of the chocolate matrix preserving thereby cocoa flavanols from degradation and oxidation. The final concentration of lycopene in 10 grams of the composite lycosome formulation of DC is 7 mg. The lycopene is in the form of tomato oleoresin from Lycored Inc. (NJ, USA) and contains 97% all trans-isomers and 3% all cis-isomers.

Volunteers will be asked to consume the investigational products in the evening with the main meal once a day for 1 month.

Blood serum specimens will be collected, processed, aliquoted and frozen at – 80°C for later analysis at both the “0” time point of the study and after 1 month of the study. All aliquots will be coded without the name of the volunteer being indicated. The identity of specimens will be known only to the Principal Investigator and the Medical Monitor.

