12.2 Record maintenance and retention

The Sponsor-Investigator will maintain records in accordance with Good Clinical Practice guidelines; to include:

- Financial disclosure information (i.e., for the Sponsor-Investigator and for sub-investigators who will be involved in the administration of the study products and/or the evaluation of research subjects [i.e., who will contribute significantly to the research study data])
- Curriculum vitae for all participants (i.e., for the Sponsor-Investigator)
- Certificates of required training; e.g., human subject protection, Good Clinical Practice, etc. (i.e., for the Sponsor-Investigator and for all sub-investigators who will be involved in the administration of the study products and/or the evaluation of research subjects [i.e., who will contribute significantly to the study data])
- Listing of printed names/signatures. (i.e., for the Sponsor-Investigator and for all sub-investigators who will be involved in the administration of the study products and/or the evaluation of research subjects [i.e., who will contribute significantly to the study data])
- Normal value(s)/range(s) for medical/laboratory/technical procedures or tests included in the clinical protocol
- Laboratory certification information
- Instructions for on-site preparation and handling of the investigational products and other study-related materials (i.e., if not addressed in the clinical protocol)
- Responsibility delegation log
- Signed informed consent forms
- Completed Case Report Forms; signed and dated by Sponsor-Investigator
- Source Documents or certified copies of Source Documents
- Monitoring visit reports
- Copies of Sponsor-Investigator correspondence (including notifications of safety information) to sub-investigators
- Subject screening and enrolment logs
- Subject identification code list

- Investigational product accountability records, including documentation of disposal.
- Final clinical study report
- Decoding procedures for blinded trials
- Master randomization list
- Retained biological specimen log
- Interim data analysis report(s)

The Sponsor-Investigator will retain the specified records and reports for up to 5 years.

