14. STUDY DISCONTINUATION CRITERIA

14.1 Discontinuation of individual research subjects

Individual research subjects can be withdrawn from the study due to occurrence of adverse effects, volunteer's request (regardless of reason) or non-compliance with the protocol. Volunteers withdrawn from the study will be replaced from the pre-screened pool of volunteers.

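### Section 12.2 orders withdrawal and replacement for any abnormal laboratory finding, although lipids and liver tests are trial outcomes, so applied as written it selects volunteers on outcome values

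*Protocol*

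**What the plan says.** Section 12.2 on withdrawal: "Any subject with adverse reaction and/or abnormal laboratory test findings will be withdrawn from the study by the Medical Officer and replaced", the replacement coming from the pre-screened pool. The instruction is mandatory, and a laboratory finding suffices without an adverse reaction.

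Section 12.1 treats laboratory findings differently: "An abnormal test finding will be classified as an *adverse event* if one or more of the following criteria are met". The criteria are accompanying symptoms, or a need for further work-up or treatment. A review decides which findings qualify, and findings thought to be study-related are followed until they resolve or stabilise.

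Section 14.1 allows withdrawal for adverse effects, the volunteer's request or non-compliance, in permissive wording and with no mention of laboratory values. It adds: "Volunteers withdrawn from the study will be replaced from the pre-screened pool of volunteers".

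The study design text in section 6 puts blood lipids in the primary endpoint. The secondary objective in 7.3.1 covers liver metabolism and blood lipids. The serum tests listed in section 6 are ALT, AST, GGT, bilirubin, triglycerides, LDL, HDL and total cholesterol, plus peroxidation products.

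On timing, section 6 says that on arrival at the site volunteers "will undergo scrupulous anamnestic, physical and laboratory investigations" and that "Study products will be given immediately after all evaluations are complete". Product is dispensed at time 0 and again at two weeks. Serum is "aliquoted and frozen at – 80°C for later analysis at both the" time-0 and 1-month points.

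The records section requires this to be kept on file: "Normal value(s)/range(s) for medical/laboratory/technical procedures or tests included in the clinical protocol".

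**The concern.** The trigger for leaving the trial overlaps with what the trial measures. A lipid or liver enzyme value outside the laboratory's range is an abnormal finding, and such values are outcomes that a study product may change. Removal can then depend on the arm and on the outcome, and those who remain are no longer the groups that were randomised.

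Two analyses named in the statistical section are exposed. The between-arm comparison loses more high values from the arms where the product does less. The paired within-arm comparison loses volunteers whose final value was high, which can look like a fall.

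An analysis plan can decide how to use data already collected. It cannot recover a 1-month sample that was never taken because a volunteer had been sent home, and that would include the stool sample needed for the primary objective. No section says that withdrawn volunteers are followed to 1 month or that their data are kept.

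**Working it through.** **Text.** The protocol gives no figure on this point, so there is none to reproduce. Three provisions stand side by side:

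| Section | Force | Laboratory findings |
|---|---|---|
| 12.1 | record, review, follow up | an adverse event only with symptoms or a need for work-up or treatment |
| 12.2 | mandatory withdrawal and replacement | any abnormal finding, no threshold, no exemption |
| 14.1 | permissive | not listed |

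The filed normal ranges give the word abnormal a workable meaning. Nothing in 12.2 adds clinical significance or change from time 0.

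**Routes after randomisation.**
1. A test during the intervention, for example at two weeks. Section 6 is compatible with this but does not clearly schedule it.
2. The 1-month value, usually known late because serum is frozen. The samples then already exist, and the rule could act only as late removal and replacement.

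An abnormality already present at time 0 is an eligibility matter and is left out.

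**Size, between arms (route 2, one test, illustration).** From the protocol: 30 volunteers and five arms. Equal allocation is assumed: 30/5 = 6 per arm, so one removal is 1/6 = 17% of an arm. The other inputs are assumed:
- time-0 value X ~ N(0,1), enrolled only if X ≤ c, where c is the limit exceeded by a share p of the source population;
- 1-month value Y = m + rX + √(1−r²)·e, with m = 0 in the comparison arm and −0.5 in the product arm;
- removed and not analysed if Y > c.

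Numerical integration at r = 0.7:

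| p | removed, comparison | removed, product | difference retained | loss | P(≥1 of 6 comparison removed) |
|---|---|---|---|---|---|
| 5% | 3.2% | 0.8% | 0.451 SD | 10% | 0.18 |
| 10% | 5.9% | 1.6% | 0.423 SD | 15% | 0.31 |
| 20% | 10.9% | 3.3% | 0.384 SD | 23% | 0.50 |

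For r between 0.5 and 0.8 the losses are 9-12%, 13-18% and 20-28%. A replacement held to the same rule restores the count, not the mean. With several tests able to trigger the rule, the chance of a removal is higher than in the last column.

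**Against sampling error.** The standard error of a difference is √(1/6 + 1/6) = 0.58 SD. The bias is 0.500 − 0.451 = 0.049 to 0.500 − 0.384 = 0.116 SD, which is 0.08 to 0.20 of one standard error. Two-sided t-test power at alpha 0.05 for 0.5 SD is about 12%, falling to 9-11%.

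**Size, within arm.** Now suppose entry is not limited to in-range values (the inclusion and exclusion criteria set no lipid limit), the product has no effect, and volunteers with Y > c are dropped. The expected change is

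E[Y − X | Y ≤ c] = −(1 − r)·φ(c)/(1 − p).

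At r = 0.7:
- p = 5%: 0.3 × 0.103/0.95 = 0.03 SD
- p = 10%: 0.3 × 0.175/0.90 = 0.06 SD
- p = 20%: 0.3 × 0.280/0.80 = 0.10 SD

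Each is a spurious fall.

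**Route 1.** Removal on an earlier value distorts the 1-month difference less, because that value is only correlated with the final one. The cost there is the missing 1-month samples, which cannot be sized from the protocol.

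**The case against.** The strongest reply is that context narrows the sentence. It stands under a heading about adverse events and directly follows the section that says when a test finding becomes one. The general discontinuation section does not list laboratory values. A sensible Medical Officer might therefore withdraw only for findings that qualify under 12.1. That may be the intent, but the wording makes laboratory findings a separate trigger, and 12.1 itself keeps findings and adverse events apart.

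Second, neither route is certain. The intermediate visit is described for dispensing and compliance questions, and 1-month serum is analysed later, when no sample can be lost and an analysis plan not shown here can decide on use of the data. This stands. A reader might infer that the rule will cost 1-month stool samples. The protocol does not support that, because it needs an on-study test that is not clearly scheduled. The shrinkage figures belong to the 1-month route and the lost samples to the other, so they should not be added together.

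Third, a reader might infer that the rule can only weaken a true effect. That is too firm. The paired comparison can show a spurious fall, and for HDL it is low values that are adverse.

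Fourth, the outcome status of these tests is mixed: section 6 puts lipids in the primary endpoint, 7.3.1 makes lipids and liver secondary, and 11.2 judges effectiveness on microbiota and oxidation markers. They are trial outcomes on any of the first two readings, which is all the point needs.

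Finally, cautious withdrawal of healthy volunteers is a legitimate safety choice. Stopping the product meets that aim without removing the volunteer from the study.

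**Conclusion.** The point holds as a defect in a conduct rule. Section 12.2 makes any abnormal laboratory finding a mandatory reason for withdrawal and replacement, conflicts with 14.1, bypasses the threshold in 12.1 and does not exempt outcome tests. Followed as written after randomisation, it selects volunteers on outcome values. It can distort both the between-arm difference and the paired change.

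The size is unknown, because the protocol gives no abnormality rate. Under the assumed model, removal on the 1-month value shrinks a 0.5 SD difference by about 10-25%, and a spurious within-arm fall of about 0.03-0.10 SD can appear at r = 0.7. Both are small beside the sampling error with 6 per arm. The effect is zero if the rule is never applied to these tests, and the between-arm and within-arm distortions vanish if all 1-month values are obtained and analysed. Loss of 1-month and microbiota samples is a possibility, not an established consequence. The case for changing the text is that the rule works against the trial's own outcomes and is cheap to correct.

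**What to change.** Amend 12.2 so that:
- the laboratory trigger covers only findings that are new or worse than at time 0 and that meet the 12.1 criteria;
- 1-month endpoint values never trigger withdrawal or replacement;
- volunteers who stop the product still give the scheduled 1-month samples if they agree, and their data stay in the analysis of the arm they were randomised to.

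Align 14.1 with this, so that both sections give the Medical Officer the same instruction.

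The cost is a short protocol amendment. No procedure is added, since the 1-month measurements are already scheduled. The downside is that some volunteers who stopped the product early stay in the analysis.

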5. LIST OF ABBREVIATIONS

6. PROTOCOL SUMMARY

Full Title: Systemic Effect of Lycosome-Formulated Dark Chocolate and GA Lycopene on Gut Microbiota, Liver Metabolism, Blood Markers of Oxidative Status and Skin Parameters in Healthy Overweight Volunteers

Short Title: Effect of Lycosome-Formulated Dark Chocolate and Lycopene on Gut Microbiota, Liver, Blood and Skin

Sample Target Size: 30

Study Population: Healthy Caucasian males and females with no acute or chronic diseases aged from 50 to 70 years with body mass index more than 30 and less than 35 kg/m².

Participating Sites:

1. Lycotec Ltd, [name]. [contact] [contact]
2. Institute of Cardiology, [name], Russia

Study Design:

The study is designed as a single, interventional, randomized clinical study to determine if one month's consumption of lycosome-formulated dark chocolate (DC) containing lycopene affects the spectrum of intestinal microbiota, blood lipids, liver parameters and oxidative status of healthy volunteers. The effects of lycopene alone and DC without lycopene addition are in the scope of the control groups as secondary objectives. All volunteers will be asked to give written consent to participation in the study and will be informed about the major goal of the study and its objectives.

The major research question to be answered in the study is whether ingestion of lycosome formulated DC or its two major constituents – lycopene and cocoa flavanols for 1 month can affect the composition of the gut microbiota, liver metabolism, blood markers of biological oxidation and skin parameters in healthy middle-aged overweight individuals.

Therefore, the primary endpoint of the project will be parameters reflecting composition of gut microbiota, blood lipids and markers of serum levels of biological oxidation – malonic dialdehyde, oxidized LDL and certain other values. The secondary endpoints will be skin parameters – sebum, corneocytes and bacterial load. Each of these parameters will be measured before trial initiation ("0" time point) and after 1 month (final point of clinical study).

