The study will be conducted following enrolment of 30 volunteers with equal representation in the study population of males and females. The study is planned to include healthy overweight individuals in the age range of 50 to 70 years old, with confirmed health status and no indication of chronic or acute disease. In particular, volunteers with history or immediate signs of

liver disease, alcoholism or intake of any medication (non-steroidal anti-inflammatory drugs, hormones, vitamins and food supplements or energy drinks) will be excluded from participation in the study. Among other exclusion criteria will be pregnancy, extensive tobacco smoking (>10 cigarettes per day), and history of cardiovascular disease. To minimize inconsistencies originating from body weight, patients with Body Mass Index (BMI) from 30 to 35 will be enrolled in the study. All volunteers will be requested to withdraw from consumption of dark chocolate, cocoa and lycopene containing products (tomatoes, ketchup etc.) for 2 weeks prior to study initiation and will be requested to ingest cocoa and lycopene-containing products strictly as mandated by the study protocol.

All study participants will undergo a preliminary anamnestic and clinical investigation. This will include reading the vital signs, determination of body mass index, anthropometry, blood pressure measurement, and electrocardiography. Among the laboratory tests will be determination of fasting serum glucose and lipids (total cholesterol, LDL cholesterol, HDL and total triglyceride levels), determination of ALT and AST level, total bilirubin, and CRP. All volunteers will be also be subject to a standard hematological investigation.

The volunteers will be randomized according to age, gender, body weight and BMI using a simple randomization method and block randomization.

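### Arms are balanced on age and gender to gain statistical strength, but the named between-arm tests ignore both factors, so little of that gain is realised

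*Protocol*

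**What the plan says.** Section 7.4.1 describes the balancing: "The groups will be balanced according to numerical age and gender with special software". It then gives the purpose of stratifying: "Stratified randomization will be used to enhance statistical strength of the final results and will ensure equality of groups for secondary selection criteria". Section 6 plans "enrolment of 30 volunteers with equal representation in the study population of males and females" and lists gender and age, with body weight and BMI, among the randomization factors.

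Section 13 (Statistical Methods/Data Analysis, under Study endpoint) names the tests. Student's t-test is for paired and unpaired samples, and for between-arm comparisons "Between-group differences at one time point will be evaluated by Wilcoxon-Mann-Whitney test (continuous variables) and Fisher's Exact test (categorical variables". The level is also fixed: "All statistical tests are two-sided and statistical significance level alpha will be set at 0.05 for the analysis". Section 10.1 treats these tests as the statistical plan and allows others only when the distribution of the data makes the listed ones unsuitable. Nothing in the protocol carries a balancing factor into the analysis.

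**The concern.** Forcing two arms to match on gender removes the gender component from the true variance of the arm difference. An unpaired t-test, a Wilcoxon-Mann-Whitney test or a Fisher's exact test on the pooled volunteers does not know this. It leaves the gender component in the error term or in the permutation distribution. The test then assumes more noise than the design leaves, rejects less often than its nominal level, and gives up most of the precision that the balancing created.

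The gain exists only where gender or age predicts the endpoint, and that is the same situation in which the named tests fail to use it. With about six volunteers per arm, a real product effect is more likely to be reported as no effect than the design requires.

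**Working it through.** **Inputs from the protocol.** Total size 30 (section 6: "Sample Target Size: 30"); five arms (section 6: "volunteers from the fifth arm will be given the regular formulation of DC without lycopene"); men and women in equal numbers; two-sided alpha 0.05.

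**Assumptions.** Equal allocation, so 30/5 = 6 per arm, with 3 men and 3 women in each. Normal outcome with within-gender SD 1. Gender explains a share f of the variance, with f from 0 to 50%. True effect 1.5 within-gender SD. The protocol gives none of these. It states no power, SD or effect size, so its figure of 30 cannot be reproduced.

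**Step 1: how far the standard error is overstated.** If gender explains share f, the difference b between men and women satisfies b² = 4f/(1 − f). With 3 men and 3 women per arm:

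- The true variance of the arm difference is 1/6 + 1/6 = 0.333. Gender cancels.
- The t-test's pooled variance also contains gender. Each arm adds 6 × (b/2)² = 1.5b² to the sum of squares. Two arms add 3b² on 10 degrees of freedom, which is 0.3b².
- The expected pooled variance is therefore 1 + 0.3b² instead of 1, and the standard error is too large by about √(1 + 0.3b²).

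At f = 25%, b² = 4 × 0.25/0.75 = 1.33, the pooled variance is 1.40 and the ratio is √1.40 = 1.18.

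**Step 2: type I error and power.** These are simulated, one pair of arms, 6 v 6. Ranges reflect separate simulation runs.

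| Share explained by gender | SE ratio | t-test type I error | t-test power | Power, same two arms, gender term |
|---|---|---|---|---|
| 0% | 1.00 | 5.0–5.1% | 65% | 64% |
| 5% | 1.03 | 4.4–4.5% | 63% | 64% |
| 10% | 1.06 | 3.8–4.0% | 60–61% | 64% |
| 25% | 1.18 | 2.2–2.4% | 51% | 64% |
| 50% | 1.48 | 0.5–0.6% | 30% | 64% |

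With the gender term, type I error stays at about 5% throughout. The exact Wilcoxon-Mann-Whitney test follows the same path: 4.1%, 3.2% and 1.9% at 0%, 10% and 25% explained. Its 4.1% at 0% is only discreteness at 6 v 6.

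**Step 3: does balancing buy power under the named tests?** At 25% explained, unadjusted t-test power is 51.1% with balanced allocation and 51.6% without it, so balancing buys nothing. On a scale that fixes the total SD, with 20% explained and an effect of 1.5 total SD:

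- t-test: 64.9% balanced against 64.2% not balanced.
- Wilcoxon-Mann-Whitney: 57.7% against 57.5%.
- Linear model with a gender term: 74%.

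At 2 total SD a small gain remains: 88.8% against 87.1% for the t-test, and 83.3% against 82.0% for the rank test. The adjusted model reaches 93.0%.

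**Step 4: dependence on balance.** If allocation is not stratified, the same tests stay at about 5.0% (t-test) and 4.1% (rank test). The conservatism comes from the balance.

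**The case against.** The strongest reply is that the premise is not settled. Section 7.4.1 attaches age and gender to balancing software, and attaches stratified randomization to secondary selection criteria. It also names simple randomization, and section 6 names simple and block randomization on four factors. Withdrawn volunteers are replaced from a pre-screened pool (sections 12.2 and 14.1) with no stated match on gender or age. Under purely simple randomization the tests hold their size. This stands, and it makes the type I error claim conditional. It does not remove the mismatch, because the text does promise balance on age and gender. Nor does the effect need perfect balance: with half the trials off by one volunteer, type I error at 25% explained was still 2.2% (rank test) and 2.7% (t-test).

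A second reply is that covariate terms are commonly left to an analysis plan that is not shown. Here the protocol names its tests and calls them the plan, so this only softens the point.

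Third, balancing also serves comparability of the groups, whatever the test. That is true, and that purpose is not in question.

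Stronger readings are tempting but not supported:

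- A reader might take the fall in t-test power from 65% to 51% as the cost of the mismatch. Most of it arises because a stronger gender effect adds variance when the within-gender SD is held fixed; it occurs without stratification too.
- A reader might quote the roughly 70% power of a five-arm model as the gain from using gender. Part of that is pooling of the error variance over five arms.
- A reader might infer that reported confidence intervals would be too wide. Section 13 plans none.

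**Conclusion.** The point holds in a conditional form. The design claims a gain in strength from balancing, and the between-arm tests fixed in section 13 cannot use it. If the balance is achieved and gender or age predicts an endpoint, those tests are conservative and almost none of the gain appears. For the t-test with arms of 6, the shortfall against a gender-adjusted analysis of the same two arms is about 1, 3 to 4 and 13 points of power at 5%, 10% and 25% of variance explained (64% less 63%, 60–61% and 51%).

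The explained share is unknown. At 0% nothing is lost. Age was not simulated, and neither was Fisher's exact test. The paired within-arm t-tests are unaffected. The error is in the conservative direction: a reader might infer that false positive findings become more likely, but the reverse is true. A reader might also infer that the whole gain is lost, but 1 to 2 points remain for very large effects.

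**What to change.** In section 13, make the main between-arm comparison of continuous endpoints one linear model over all five arms with arm and gender as terms, on a transformation or on ranks fixed in advance, and take the arm contrasts from it. If a rank test is preferred, use the gender-stratified Wilcoxon (van Elteren) test. Keep the unstratified tests as sensitivity analyses.

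Add continuous age only in the five-arm model. That model has 30 − 5 − 1 = 24 error degrees of freedom with gender and 23 with age. A two-arm model has 12 − 2 − 1 = 9, and there an age term cost about 6 points of power when age was unrelated to the outcome and left unbalanced.

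Reconcile the randomization descriptions in sections 6 and 7.4.1, so that the factors in the analysis are those actually used in the allocation.

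The change is one of wording and needs no new data. A gender term costs about 1 point of power (65% to 64%, two arms) if gender is unrelated to the endpoint, and it brings a model assumption. The van Elteren test costs more in that case, about 4 points at 1.5 SD (58.4% to 54.3%), and gains only about 1 point at 10% explained (58% to 59%), so the linear model is the better default.
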